10.3.3. Estimation of the Propensity Score

A PS is the probability of receiving treatment given an observed set of known covariates, which can be used to balance covariate values between the treated and control participants to obtain an unbiased estimate of treatment effect.

The PS in this analysis represents the probability of participants being in the Roctavian cohort given the observed set of baseline participant characteristics. This will be calculated using a logistic regression model predicting treatment assignment from baseline characteristics.

Propensity scores will be developed based on baseline characteristics of the study cohorts (see Section 10.2) described in Table 3 and Table 4. Potential variables for inclusion in the PS have been identified based upon variables from a literature review of factors associated with bleeding, previous PS development for a comparison of Roctavian to FVIII prophylaxis based on studies that were part of the Roctavian clinical development (Liu 2022; Oldenburg 2024; see Appendices for further details), and clinical input from health care practitioners

(HCPs) in Germany managing PwSHA. Statistical relationships between potential variables and treatment cohort (as defined in the SAP) for the study data, along with clinical input on variables to include regardless of statistical relationship will be utilized to select variables included in the propensity score.

10.3.3.1. Variable identification based on literature, previous work, and clinical HCP input

Prior to the initiation of data collection, a comprehensive literature review was conducted to identify the risk factors or covariates associated with bleeding events among PwSHA. No real world data is currently published on characteristics associated with usage of gene therapy compared to other hemostatic therapies. The findings from this review identified a list of potential variables to be assessed in the PS. The comprehensive literature review was designed to capture the most relevant and high-quality studies based on a fit-for-purpose search strategy developed using key words, MeSH terms, and Boolean operators. There were no date or geographic restrictions for the search, but only articles published in English were included. In addition, meeting abstracts were also excluded. After a comprehensive search strategy was developed (see [Appendices](#) for details), the search was executed on November 21, 2023, across the following online databases: Embase, OVID Medline, and the Cochrane Library (CDSR/CENTRAL).

Utilizing the Population, Intervention, Control, Outcome, and Study Design (PICOS) framework, fit-for-purpose study selection criteria was developed (see [Appendices](#)). Study selection was conducted in two phases, title/abstract screening, and full-text screening. The initial title and abstract screening was completed by one reviewer (using a conservative approach – including articles that might have missing/unsure PICOS criteria), while subsequent full-text screening was completed by two independent reviewers, where conflicts were resolved between the two reviewers. In addition to the PICOS criteria, only articles that examined the association between HA treatment and bleeding events while considering covariates, either as part of the study design (ie, pre-randomization stratification or matching) or adjustments in the analysis, were included.

A data extraction form was created, and pilot tested including information on study characteristics, patient characteristics/study population, analysis details, and covariates considered in the study design or analysis of included studies. Once the data extraction form was pilot tested, the first reviewer extracted data based on the presented columns, while the second reviewer verified all the extracted data for quality assurance purposes. see [Appendices](#) for further details for data extraction fields. After completion of the data extraction, a qualitative synthesis of the included articles was conducted to summarize the articles included in the literature review and to recommend a list of covariates to include in the PS. Overall, the comprehensive literature review included 14 unique studies for covariate assessment. After HCP expert review, one additional study ([Chowdary 2022](#)) was also considered to provide recommendations for covariates to include in the PS in order to

complement the results from the comprehensive literature review. This study used predictive modeling to identify predictors of long-term ABR during prophylaxis with EHL FVIII.

In addition to the comprehensive literature review results, HCP expert advice and previous work on developing PS for the comparison of Roctavian to FVIII prophylaxis ([Liu 2022](#); [Oldenburg 2024](#); see [Appendices](#) for further details) has informed/confirmed the list of potential variables to assess for inclusion in the PS. In particular, HCPs in Germany treating PwSHA with either Roctavian or SoC products advised the study team regarding overall study conduct and interpretation, as well as providing input into variables identified for PS inclusion. HCPs provided input into variables both associated with the endpoint of bleeding events as well as factors associated with choosing Roctavian treatment.

[Table 9](#) outlines the potential variables to include in the PS based on the comprehensive literature review, expert physician input, and prior comparative Roctavian versus FVIII prophylaxis studies PS development along with considerations for inclusion based on clinical relevance, potential statistical associations, and anticipated correlations between variables. Prior bleeding history, ABR (12 months prior to index date), will be included in the PS regardless of statistical significance due to clinical significance based on feedback from German physicians. See the SAP for further information regarding operationalization of the variables for PS assessment in the SAP.

Table 9: List of potential variables for inclusion in PS

Variable	Literature review	From previous PS work	Clinical expert opinion	Considerations
Baseline/prior bleeding history (eg, ABR)	✓	✓	✓	Include regardless of statistical association, based on clinical relevance
Baseline FVIII utilization	✓	✓	✓	Include based on statistical association and correlation with other variables (eg, baseline/prior bleeding history and baseline prophylaxis class)
Baseline prophylaxis class (FVIII vs. emicizumab)	✓	✓	✓	Include based on statistical association and correlation with other variables (eg, baseline/prior bleeding history and FVIII utilization)
Age	✓	✓	✓	Include based on statistical association
Height, Weight and/or BMI	✓	✓	✓	Include based on statistical association
Baseline von Willebrand factor (IU/mL)	✓	X	✓	Include based on statistical association
Number of target joints	✓	✓	X	To be considered depending on statistical association and correlation with other variables (eg, baseline/prior bleeding history and joint health score)
Joint health (eg, baseline/prior HJHS)	X	X	✓	To be considered depending on statistical association and correlation with other variables (eg, baseline/prior bleeding history and number of target joints)
Baseline/prior type of bleeds	X	X	✓	To be considered depending on statistical association and correlation with other variables (eg, baseline/prior bleeding history and target joints)
Geography (HTC/site/region/country)	✓	✓	X	Site to be considered depending on statistical association and correlation with other variables
Prophylaxis class switching (eg, SHL/PD to EHL/emicizumab)	✓	✓	X	To be considered depending on statistical association and correlation with other variables

Variable	Literature review	From previous PS work	Clinical expert opinion	Considerations
Baseline/prior pain (eg, BPI-sf)	X	X	✓	To be considered depending on statistical association and correlation with other variables (eg, target joints and HJHS)
Baseline/prior QoL (eg, Haemo-QoL-A)	X	X	✓	To be considered depending on statistical association and correlation with other variables
Activity status	X	X	✓	Not considered as this there is no validated questionnaire for lifestyle factors in PwSHA
Baseline/prior history of liver fibrosis/cirrhosis	✓	X	X	Significant liver fibrosis/cirrhosis is accounted for by the exclusion criteria, but less severe liver fibrosis to be considered based on statistical association
Baseline/prior history of hepatitis B and C	✓	X	X	Not considered as this is accounted for by study exclusion criteria
Baseline/prior history of HIV positivity	✓	X	X	Include based on statistical association
Baseline/prior history of cancer	✓	X	X	Include based on statistical association
Baseline/prior history of hypertension	✓	X	X	Include based on statistical association
Baseline/prior history of osteoporosis	✓	X	X	Include based on statistical association
Adherence to treatment	✓	X	X	Not considered as there is not enough prior literature/evidence to suggest as factor related to bleeding outcomes; confirmed by clinical expert
Genotype	X	X	X	Not considered as this is a factor for inhibitor development but not bleeding outcomes and accounted for by study exclusion criteria for history of or current inhibitors

ABR, Annualized bleeding rate; BMI, body mass index; EHL, extended half-life; FVIII, coagulation factor VIII; HIV, human immunodeficiency virus; HTC, hemophilia treatment center; PD, plasma-derived; PwSHA, people with severe hemophilia A; QoL, quality of life; SHL, standard half-life.

Note: Other variables identified in the literature review but not outlined in [Table 9](#), due to lack of relevance to this study and the association comparing Roctavian and SoC and bleeding outcomes, were ethnicity, treatment duration, pharmacokinetic (PK)-guided dosing use, prophylaxis vs on-demand treatment, concurrent medications (bypass agents, non-steroid anti-inflammatory drugs, tranexamic acid, and corticosteroid), and hemophilia severity.

Proprietary and Confidential

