5.2.2. Exclusion Criteria

Individuals are excluded from the study if any of the following criteria apply:

- Is currently in, or previously participated (in the last 12 months before index), an interventional clinical trial involving an investigational product to treat HA
- History of inhibitors against FVIII ever (or current) as recorded in the DHR prior to index
- Presence of acute infections (such as acute respiratory infections or acute hepatitis) or uncontrolled chronic infections (such as chronic active hepatitis B), and/or known significant hepatic fibrosis or cirrhosis at index

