7.2.3. Demographic Information and Clinical History

Demographic information, comorbid conditions and clinical history will be derived from data entered into the DHR prior to and/or at index date. These variables will be utilized to identify and describe participants in the study cohorts, as well as being considered for inclusion in the PS. Variables collected in the DHR (at the time of protocol drafting) that will be utilized to characterize the study cohorts regarding demographic information, location of hemophilia management and participation in clinical trials are describe in [Table 3](#), with variables to characterize participants clinical history, including hemophilia history, described in [Table 4](#).

Table 3: Demographic Information

Variable	Description	Captured in DHR	Time period for Analysis	Entry into DHR	Operational notes including Relevant Data Fields in DHR
Age	Approximate age of participant	✓	At index	At enrollment	
Date of birth (month/year) is collected in DHR, but only year is available for analysis per DHR practices.
 
Inclusion criteria of aged ≥ 18 years of age at index and confirmed at time of enrollment based on DHR field confirming that the participant fulfills the AbD inclusion/exclusion criteria.
 
Study participants will be described based on categorial intervals for year of birth (5-year increments).
 
An assumed day and month of birth (eg, 1 July) for all participants will be implemented to describe approximate age of participants at index.
 
Ability to collect month or date of birth were discussed with the registry though collection of this potential personally identifiable information are not possible based on DHR practices.

Gender	Male gender	✓	--	At enrollment	
Confirm inclusion criteria. Inclusion criteria additionally confirmed at time of enrollment based on DHR field confirming that the participant fulfills the AbD inclusion/exclusion criteria.

Height	Height in cm	✓	At index or during baseline	Ongoing	
Description of cohorts, based on recording closest to or at index

Weight	Weight in kg	✓	At index or during baseline; follow-up	Ongoing	
Description of cohorts, based on recording closest to or at index
 
Data will additionally be utilized to derive treatment utilization data (see Table 7).

Variable	Description	Captured in DHR	Time period for Analysis	Entry into DHR	Operational notes including Relevant Data Fields in DHR

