Hepatitis C Virus (HCV) status	History of HCV, along with treatment of infection	✓	Any time prior to index	Ongoing	Description of cohorts. Based on HCV status recorded in the DHR, including but not limited to: History of HCV (cured infection vs no infection history) Treatment for HCV eradication during baseline Presence of acute or uncontrolled chronic hepatic infections at index is an exclusion criteria. HCV status as documented in the DHR will be used to describe the population, as well as confirm inclusion/ exclusion criteria. Exclusion criteria will additionally confirmed at time of enrollment based on DHR field confirming that the participant fulfills the AbD inclusion/exclusion criteria.
Chronic liver disease status	Presence of liver fibrosis and/or cirrhosis	✓	Baseline	Ongoing	Description of cohorts. Based on liver disease (eg, report of fibrosis) recorded in the DHR. Presence of known significant hepatic fibrosis or cirrhosis at index is an exclusion criteria, which will be confirmed at time of

Variable	Description	Captured in DHR	Time period for Analysis	Entry into DHR	Operational notes including Relevant Data Fields in DHR
					enrollment based on DHR field confirming that the participant fulfills the AbD inclusion/exclusion criteria. Definitions of acute liver failure (Tholey 2023), liver fibrosis and/or progression of liver fibrosis (Lee 2022a), or cirrhosis (Lee 2022) will be consistent with MSD Manuals for classification. Fibrosis status as documented in the DHR will be used to describe the population.

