Median	0		0		0.0000	0		0		0.0000		
Q1	0		0			0		0				
Q3	0		0			0		0				
Min	0		0			0		0				
Max	0		0			0		0				
Weight (kg)												
Mean	0.00		0.00		0.0000	0.00		0.00		0.0000	0.00	
SD	0.00		0.00			0.00		0.00				
Median	0		0		0.0000	0		0		0.0000		
Q1	0		0			0		0				
Q3	0		0			0		0				
Min	0		0			0		0				
Max	0		0			0		0				
BMI												
<18.50	0	0.0%	0	0.0%	0.0000	0	0.0%	0	0.0%	0.0000	0.00	
18.50 - <25.00	0	0.0%	0	0.0%		0	0.0%	0	0.0%			
25.00 - <30.00	0	0.0%	0	0.0%		0	0.0%	0	0.0%			
≥30.00	0	0.0%	0	0.0%		0	0.0%	0	0.0%			
HCV infection												
No infection	0	0.0%	0	0.0%	0.0000	0	0.0%	0	0.0%	0.0000	0.00	
Active and/or cured infection	0	0.0%	0	0.0%		0	0.0%	0	0.0%			
Unknown	0	0.0%	0	0.0%		0	0.0%	0	0.0%			
Chronic liver disease												
Liver fibrosis	0	0.0%	0	0.0%	0.0000	0	0.0%	0	0.0%	0.0000	0.00	
Liver cirrhosis	0	0.0%	0	0.0%		0	0.0%	0	0.0%			
Not specified/ unknown	0	0.0%	0	0.0%		0	0.0%	0	0.0%			

Measures	Unadjusted						After IPTW					
	Roctavian Cohort		SoC Cohort		p-value (Roctavian vs. SoC)	Std. Diff. (Roctavian vs. SoC)	Roctavian Cohort		SoC Cohort		p-value (Roctavian vs. SoC)	Std. Diff. (Roctavian vs. SoC)
	N=		N=				N=		N=			
	N	(%)	N	(%)	N	(%)	N	(%)				
Other comorbidities												
Malignancy	0	0.0%	0	0.0%	0.0000	0.00	0	0.0%	0	0.0%	0.0000	0.00
Hypertension	0	0.0%	0	0.0%			0	0.0%	0	0.0%		
Osteoporosis	0	0.0%	0	0.0%			0	0.0%	0	0.0%		
Von Willebrand factor (IU/mL)												
Mean	0.00		0.00		0.0000	0.00	0.00		0.00		0.0000	0.00
SD	0.00		0.00				0.00		0.00			
Median	0		0		0.0000		0		0		0.0000	
Q1	0		0				0		0			
Q3	0		0				0		0			
Min	0		0				0		0			
Max	0		0				0		0			
Target joints												
Yes	0	0.0%	0	0.0%	0.0000	0.00	0	0.0%	0	0.0%	0.0000	0.00
No	0	0.0%	0	0.0%			0	0.0%	0	0.0%		
Unknown	0	0.0%	0	0.0%			0	0.0%	0	0.0%		
Number of target joints												
Mean	0.00		0.00		0.0000	0.00	0.00		0.00		0.0000	0.00
SD	0.00		0.00				0.00		0.00			
Median	0		0		0.0000		0		0		0.0000	
Q1	0		0				0		0			
Q3	0		0				0		0			
Min	0		0				0		0			
Max	0		0				0		0			
Prophylaxis type												
FVIII only	0	0.0%	0	0.0%	0.0000	0.00	0	0.0%	0	0.0%	0.0000	0.00
Non-factor products only (e.g., emicizumab)	0	0.0%	0	0.0%			0	0.0%	0	0.0%		
FVIII and non-factor products	0	0.0%	0	0.0%			0	0.0%	0	0.0%		
SoC switch												
SHL to EHL	0	0.0%	0	0.0%	0.0000	0.00	0	0.0%	0	0.0%	0.0000	0.00
	0	0.0%	0	0.0%	0.0000	0.00	0	0.0%	0	0.0%	0.0000	0.00

Measures	Unadjusted						After IPTW					

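### Hepatitis B/C history is left out of the propensity score candidates on the ground that eligibility accounts for it, but the exclusion covers only acute or uncontrolled infection, so cured HCV can still vary between cohorts

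*Protocol*

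**What the plan says.** Protocol Section 10.3.3.1, Table 9, lists prior history of hepatitis B and C as a factor found by the literature review and disposes of it with "Not considered as this is accounted for by study exclusion criteria". SAP Section 7.8.2.1, Table 6, repeats the entry.

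The criterion relied on is in Protocol Section 5.2.2 (SAP 7.3.5.2). It excludes on "Presence of acute infections (such as acute respiratory infections or acute hepatitis) or uncontrolled chronic infections (such as chronic active hepatitis B") and on known significant fibrosis or cirrhosis, all judged at index. Protocol Table 4 restates it for HCV: "Presence of acute or uncontrolled chronic hepatic infections at index is an exclusion criteria".

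The same Table 4 entry plans to describe the cohorts by "History of HCV (cured infection vs no infection history"). SAP Table 3 gives cured infection as one of the HCV status categories, and the baseline clinical shell in SAP Section 12.1 has a row for "Active and/or cured infection" in both cohorts.

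Protocol Section 7.2.3 says that the demographic and clinical history variables, HCV status among them, serve to describe the cohorts "as well as being considered for inclusion in the PS". Section 10.3.3 likewise builds the PS from Tables 3 and 4. In Table 9 the fibrosis row notes that significant disease is excluded, "but less severe liver fibrosis to be considered based on statistical association". HIV history is a candidate on the same terms.

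**The concern.** A variable is accounted for by eligibility only if eligibility removes its variation. An exclusion for current acute or uncontrolled infection leaves in everyone whose infection was cured and, on the wording, anyone whose chronic infection is controlled. If past hepatitis is unevenly spread between the cohorts, the weights are not built to balance it.

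There are reasons to expect it to matter. The literature review behind Table 9 looked for covariates in studies of treatment and bleeding, and hepatitis history is ticked there. The vector acts in liver cells (Protocol Section 3.2.2.1), so past hepatitis could plausibly influence who is offered it; that step is inference, not something the documents state. Severe liver disease, hospitalization and death are compared under the same weights.

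**Working it through.** The plan gives no HCV prevalence and no effect of HCV history on any outcome, so there is no figure of its own to reproduce. The sample size does not depend on this point. The check is textual first, then a range under stated assumptions.

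**Does eligibility remove the variation?**

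- Section 5.2.2 excludes FVIII inhibitors ever or current, but infections only if present at index and acute or uncontrolled. Where a history is meant to exclude, the list says so. For hepatitis it does not.
- Table 4, SAP Table 3 and the SAP shell all provide for cured HCV among those analysed.
- The fibrosis row meets the same partial exclusion and keeps the remainder as a candidate. The hepatitis, fibrosis and HIV rows carry the same source marks (literature yes, previous PS work no, expert opinion no), so the marks do not explain the different treatment.

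The stated reason is therefore wrong.

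**What else could catch an imbalance?**

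- Protocol 10.3.4.1 recalculates standardized mean differences (SMDs) after weighting for variables outside the PS too, but makes the PS variables the focus.
- SAP 7.8.2.3 refines the PS, including by adding covariates, if an SMD above 0.25 remains.
- SAP 7.9.3, and SAP 7.9.4.5 for the treatment policy safety models, bring covariates still imbalanced into the outcome model.
- SAP 7.9.4.3 (hemostatic use) specifies weighted t-tests and Chi-square tests, and SAP 7.9.4.5 specifies weighted rate ratios for hypothetical-estimand safety. Neither states an adjusted model.

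**Illustration.** Let p1 and p0 be the proportions with cured HCV in Roctavian and SoC, and g the outcome ratio for HCV history. All are assumptions.

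SMD = |p1 − p0| / √{[p1(1 − p1) + p0(1 − p0)] / 2}

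- 0.20 v 0.40: 0.20 / √[(0.16 + 0.24)/2] = 0.447
- 0.30 v 0.40: 0.10 / √[(0.21 + 0.24)/2] = 0.211
- 20-point gaps from 0.10 v 0.30 to 0.30 v 0.50: 0.516 to 0.417

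Spurious ratio with no treatment effect = [1 + p1(g − 1)] / [1 + p0(g − 1)]

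| Outcome | p1 v p0 | g | Ratio |
|---|---|---|---|
| Bleeding | 0.20 v 0.40 | 1.2 | 1.04/1.08 = 0.96 |
| Bleeding | 0.10 v 0.30 | 2.0 | 1.10/1.30 = 0.85 |
| Bleeding | 0.30 v 0.40 | 2.0 | 1.30/1.40 = 0.93 |
| Bleeding | 0.40 v 0.20 | 1.2 | 1.08/1.04 = 1.04 |
| Bleeding | 0.40 v 0.20 | 2.0 | 1.40/1.20 = 1.17 |
| Liver event | 0.20 v 0.40 | 3 | 1.40/1.80 = 0.78 |
| Liver event | 0.20 v 0.40 | 5 | 1.80/2.60 = 0.69 |
| Liver event | 0.40 v 0.20 | 3 | 1.80/1.40 = 1.29 |
| Any | equal | any | 1.00 |

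These are crude values, with nothing adjusted. The 0.30 v 0.40 case is the most instructive: if weighting left that gap in place, its SMD of 0.21 would exceed 0.1 without triggering the SAP's PS refinement.

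**The case against.** The strongest reply is that the plan does not depend on this row. HCV infection sits in the baseline shell with a standardized difference before and after weighting, so an imbalance would be seen. The SAP allows covariates to be added to the PS above 0.25 and imbalanced covariates to enter the bleeding and treatment policy safety models, and SAP 7.9 says in general terms that multivariable models will be reported if more adjustment is needed to balance the cohorts. Sections 7.2.3 and 10.3.3 even put HCV status forward for the PS. Age and milder fibrosis are candidates and may carry part of any HCV effect. The protocol already concedes in Section 10.5 that the PS is weaker for rare safety events, and SAP Table 5 describes malignancy regardless of relationship to treatment without comparing it.

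Most of this stands. A reader might infer that HCV history can never be adjusted for, or that the confounding is concealed. The documents do not support either reading: the balance tables expose it and several rules could bring it in.

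What the reply does not rescue is the row itself. The fallback rules are conditional, the balance review is pointed at the PS variables, and someone told that hepatitis is already dealt with has little reason to act on it. That other sections put HCV status forward while Table 9 rejects it is a contradiction to resolve, not a safeguard.

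**Conclusion.** The point holds as an error in the stated reason and an inconsistency in the candidate list. Eligibility does not account for hepatitis history; it removes only acute or uncontrolled infection at index. The consequence is largest where the weights are the only adjustment the section states (hemostatic use, hypothetical-estimand safety rate ratios) and where an SMD settles between 0.1 and 0.25.

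It would be tempting to conclude that the comparison is biased in favour of Roctavian. The documents do not allow that. Under the assumed inputs the spurious bleeding ratio runs from 0.85 to 1.17 depending on which cohort has more cured HCV, and it is 1 if the proportions are equal. The liver-event ratios of 0.78 and 0.69 rest on assumed risk multiples of 3 and 5 and on no adjustment at all. They show that the effect could matter, not that it does.

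**What to change.** In Protocol Table 9 and SAP Table 6 replace the entry with: *Acute and uncontrolled infection is covered by the exclusion criteria; history of HCV (cured vs none) to be included based on statistical association.* This puts it on the same terms as the fibrosis and HIV rows and brings Table 9 into line with Protocol Sections 5.2.2, 7.2.3 and 10.3.3. Derive it from the registry HCV status field in Protocol Table 4 and SAP Table 3, which separates cured from active infection; the shell row that pools the two would not serve.

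Hepatitis B needs separate handling because neither baseline table lists a field for its history. Treat it the same way only if the registry records it; otherwise name it as an unmeasured factor in the limitations.

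No separate adjustment threshold is needed, since the SAP already provides for adjusting imbalanced covariates. The cost is one table row in each document, no new HCV data collection and no change in sample size. The SAP's backward selection can drop the variable if it is unrelated to treatment.
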